7.2 Setting

Physician Selection:

This study will be carried out with specialist hematologists, internists, pediatricians or physicians working at specialized thalassemia centers, with a pediatric NTDT patient population and an interest in participating in such an observational study. These physicians were identified after detailed site selection visits at thalassemia centers located in countries with high prevalence of thalassemia. All sites have previously participated in thalassemia clinical research programs and have sufficient experience in treatment of these patients.

Prior to study site selection, Novartis representatives reviewed the protocol with potential physicians at the center and an informed decision was taken by the physician whether or not to participate.

Population:

A minimum of 40 patients who currently are (maximum of 12 months) or are planned to be treated with deferasirox, will be enrolled in this registry. At least 20 patients will be enrolled for the two age categories (10 to \leq 12 and \geq 12 to \leq 18).

Each physician participating in the study will approach all the eligible NTDT patients for the study who meet the criteria for inclusion and non-inclusion. In addition, patient database at the site will be reviewed to identify patients who may potentially qualify for the study.

Furthermore, the source of patient recruitment could be referral from other practices, friends/family member referral, via advocacy groups, etc.

A least 40 patients will be sufficient to evaluate the safety of deferasirox in the pediatric NTDT population. According to the Guidelines for the treatment of NTDT, data on the global epidemiology of the thalassemias, especially NTDT, are scarce. Some 23,000 children are born with transfusion-dependent β-thalassemia major each year, while a smaller ill-defined number have the NTDT form β-thalassemia intermedia. The prevalence of non-transfusion-dependent thalassemia patients with clinically significant iron overload is assumed to be 2 - 14% of the total number of transfusion-dependent thalassemia patients).

In NTDT, a combination of increased intestinal iron over-absorption and occasional transfusions results in an iron accumulation rate which is much slower than in patients with transfusion dependent thalassemias. As a result, patients with NTDT tend to present with some degree of iron overload later in their life compared to transfusion dependent patients. This fact limits the pool of patients who could potentially meet the eligibility criteria and be enrolled in to the study. Furthermore, the feasibility which was conducted in major thalassemia countries

confirmed the limited number of pediatric patients with NTDT who can be treated with deferasirox.

Patients will be enrolled if they meet the following criteria.

Inclusion criteria:

Patients eligible for inclusion in this study must meet all of the following criteria:

1. Male or female aged \geq 10 but <18 years old with non-transfusion-dependent thalassemia syndromes inclusive of beta-thalassemia intermedia, HbE beta-thalassemia or alpha thalassemia intermedia (HbH disease) and chronic iron overload

AND

2. Patients currently treated for a maximum of 12 months or patients planned to be treated with deferasirox

AND

3. Written informed consent obtained prior to any screening procedures. The consent form will be signed by the patient's legal guardian.

Exclusion Criteria

1. Patients treated with deferasirox in an interventional clinical study.

7.3 **Variables**

Treatment

Treating the Patient

The study being non-interventional, the patient will be treated at the physician's discretion and according to the local country-specific deferasirox prescribing information.

The starting dose of deferasirox, subsequent dose adjustments and treatment interruption will be at the physician's discretion and according to the local country-specific prescribing information and will be recorded on the Dosage Administration Record eCRF together with the reasons for the dose changes and interruptions.

Drug Compliance

The compliance will be assessed by caregiver interviews. The caregiver will be asked how many doses, if any, of deferasirox treatment was missed in the last treatment period.

Drug Accountability

Not applicable since commercial drug is used.

IWR (Interactive Web Response System)

The physician or designated staff will contact the IWR and provide the requested identifying information for the patient to register them into the IWR. Once assigned, the Patient Number must not be reused for any other patient and the Patient Number for that individual must not be

The key eligibility criteria will be checked via IWR.

changed, even if the patient is re-screened.

If the patient fails to be enrolled in the trial for any reason, the reason will be entered into the Screening Log.

IWR must be notified within 2 days that the patient was not enrolled.

Visit schedule and assessments

Study flow and visit schedule

This study is non-interventional and does not impose a therapy protocol, diagnostic/therapeutic interventions or a strict visit schedule. The frequency of assessments will be according to the physician's judgment and in accordance with the local country- specific deferasirox prescribing information. If the data is available, it is suggested that the treating physician complete the appropriate eCRFs at a minimum of every 3 months. Below is the recommended assessment schedule.

Retrospective data collection will be done for patients whom have started deferasirox 12 months or less prior to enrollment.

The baseline is defined as the timeframe before the patient starts treatment with deferasirox.

In patients who have protocol specified assessments performed prior to the date of first deferasirox treatment, the baseline data will be collected if it is within the following timeframe prior to the date of starting deferasirox treatment (see also table 7-2):

- 1.5 months for all laboratory assessments
- 6 months for vital signs, weight, height, LIC ECG, ECHO, CMR, ocular and audiometry assessments
- 12 months for pubertal assessments (Tanner stage).

Post baseline data will be collected from the start date of deferasirox and then on for five years.

Table 7-2 Suggested Schedule of Assessments

	At Baseline / Enrollment	At each visit	Discontinuation / End of Study		
Obtain Inform Consent	Х				
Demographics	Х				
IRW	Х				
Inclusion / Exclusion Criteria	Х				
Medical History	X*				
Previous Iron Chelation History	X*				
Transfusion / RBC History	X*				
Physical Exam ⁴	Х	Х	Х		
Height ⁴	X ¹	Х	Х		
Weight ⁴	X ¹	Х	Х		
Vitals ⁴	Х	Х	Х		

	At Baseline / Enrollment	At each visit	Discontinuation / End of Study
Sexual development assessment (Tanner stage) 4	X ²	Х	Х
ECG ⁴	X ¹	Х	Х
ECHO ⁴	X ¹	Х	Х
CMR ⁴	X ¹	Х	Х
Ocular Exam ⁴	X ¹	Х	Х
Audiometry ⁴	X ¹	Х	Х
LIC	Х	Х	Х
Laboratory Assessments:			
Hematology ⁴	X ³	Х	Х
Biochemistry ⁴	X ³	Х	Х
Hepatitis Viral ⁴	X ³	Х	Х
Serum Ferritin	X ³	Х	Х
Serum Creatinine ⁴	X ³	Х	Х
ALT/AST ⁴	X ³	Х	Х
Bilirubin ⁴	X ³	Х	Х
Alkaline Phosphatase ⁴	X ³	Х	Х
Urea ⁴	X ³	Х	Х
Creatinine Clearance ⁴	X ³	Х	Х
Proteinuria determination (urinalysis dipstick, urinary protein/urinary creatinine) ⁴	X ³	X	X
Serum pregnancy test ⁴	X ³	X	Х
Urinary pregnancy test ⁴	X ³	X	X
Transfusions	X*	Х	X
Concomitant Medication	X*	Х	X
Adverse Events	X	Х	Х
Dose administration Record (DT)	X	Х	Х
Dose administration Record (FCT)	Χ	Х	X
End of Study/Study completion			Х

^{*}For patients already treated with deferasirox, transfusion, concomitant medications and concomitant diseases will be collected at enrollment.

¹Baseline assessments will be collected if performed within 6 months prior to the start date of deferasirox treatment.

²Baseline pubertal assessment (Tanner stage) will be collected if performed up to 12 months prior to the start date of deferasirox treatment.

³Baseline assessments will be collected if performed within 1.5 months prior to the start date of deferasirox treatment.

⁴Assessments considered to be safety assessment.

Screening examination

Eligibility screening

The physician will review the patient medical file to assess whether he or she is eligible for participation in the surveillance study.

Information to be collected on screening failures

None.

Patient demographics and other baseline characteristics

The following baseline information will be collected where available within the timeframe provided in table 7-2:

- Date of birth, gender, race, and ethnicity
- Medical history and disease characteristics
- History of previous iron chelation
- History of transfusion in the 12 months prior to the start of deferasirox treatment
- Baseline laboratory assessments such as serum creatinine (SrCr), creatinine clearance, SF, urea, SGOT (AST), SGPT (ALT), alkaline phosphatase, bilirubin and proteinuria.
- Baseline vital signs, weight, height, sexual development assessment, ECG, echocardiography, cardiac magnetic resonance (CMR), and LIC.

For patients already treated with deferasirox, transfusion, concomitant medications and concomitant diseases will be collected at enrollment.

Treatment period

This study is a non-interventional study and therefore does not impose a treatment period. Patients will be treated with deferasirox according to the physician's judgment and in accordance with the local country-specific deferasirox prescribing information. The daily dose of deferasirox will be recorded by the physician and/or study personnel, this will include the initial dose of deferasirox and subsequent changes in dose. The maximum treatment duration of deferasirox treatment observed will be 5 years.

Compliance will be recorded by the physician from information provided retrospectively by the parent/caregiver.

Effectiveness

According to the general prescribing information for deferasirox, measurements of SF should be performed monthly to assess response to therapy and to evaluate for the possibility of overchelation of iron. All available SF values will be recorded.

Premature withdrawal

Patients must be withdrawn from the study if any of the following occurs:

Consent withdrawal

- Deferasirox treatment permanently stopped, except due to stopping rule.
- Patient participating in an interventional clinical trial

Patients may voluntarily withdraw from the study or be dropped from it at the discretion of the physician at any time.

For patients who are lost to follow-up, the physician should show "due diligence" by documenting in the source documents steps taken to contact the patient, e.g. dates of telephone calls, registered letters, etc.

Follow up period

Data will be collected on each patient for up to 5 years from the start of deferasirox treatment. There is no follow-up period after the 5 years unless the patient discontinued due to an adverse event (in this case refer to Section 9).

Assessment types

Safety

Patient safety will be monitored by reviewing medical and laboratory records and collecting available data on:

- SrCr, creatinine clearance, SF, urea, SGOT (AST), SGPT (ALT), alkaline phosphatase, bilirubin and proteinuria,
- LIC, CMR, echocardiography, ECG, vital signs,
- cardiac events potentially related to cardiac iron overload,
- height, weight, BMI,
- sexual development according to Tanner stage,
- audiometry and ophthalmology examination findings,
- concomitant medication at time of renal or hepatic AE,
- adverse event (AE)

For details on AE collection and reporting, refer to Section 9.

Laboratory evaluations

All local laboratories contributing to the study should provide the sponsor with a copy of the laboratory's certification and a tabulation of the normal ranges and standard deviations from control values for each of the parameters being evaluated. These laboratory references should be forwarded to the sponsor prior to study start and updated promptly if any information changes during the course of the study.

Data on the following parameters will be collected when available:

- serum creatinine
- creatinine clearance (the method used by the site to check the creatinine clearance will also be collected)
- serum ferritin

- urea
- SGOT (AST)
- SGPT (ALT)
- alkaline phosphatase
- bilirubin
- proteinuria (the method used by the site to check the proteinuria will also be collected)

Renal biopsy

Information on renal biopsies will be collected when available.

Cardiac parameters

Information on blood pressure, pulse, ECG, echocardiography and CMR will be collected when available.

Information on cardiac events that meet the definition of Serious Adverse Event must be reported as described in Section 9.

A list of cardiac events potentially related to cardiac iron overload is provided below:

- Sudden cardiac death
- Cardiac arrhythmias
- Congestive heart failure
- Cardiomyopathy
- Pulmonary hypertension

Liver iron concentration

Information on LIC and the method of its assessment will be collected when available.

Auditory and ophthalmology

The Prescribing Information recommends annual audiometry and ophthalmology examinations. The examination dates and findings (normal or not) will be collected on the audiometry and ophthalmology eCRF. Information about the examination must be present in the source documentation at the study site. Findings that meet the definition of an adverse event must also be recorded in the AE eCRF.

Transfusion requirements

Blood transfusion requirements will be collected if available.

7.4 **Data sources**

Initiation of the participating sites will be performed by Novartis and/or a designated CRO. Before study initiation, a Novartis representative (or designee) will review the protocol and eCRF with the physicians and their staff.

Sites enrolling patients in this study will record data on eCRFs provided by Novartis (or designee) which will capture, check, store and analyze the data.

CROs (if utilized) will follow their own internal SOPs that have been reviewed and approved by Novartis.

Concomitant or prior medications entered into the database will be coded using the World Health Organization (WHO) Drug Reference List. Medical history/current medical conditions and adverse events will be coded using the Medical dictionary for regulatory activities (MedDRA) terminology.

Safety data will be transferred to Novartis at a frequency as defined in Section 9 of this protocol and/or CRO contract. Clinical data will be transferred to Novartis after closure of the study.

Data collection schedule

This is a non-interventional study and does not impose a therapy protocol, diagnostic/therapeutic procedure, or a visit schedule. Patients will be treated according to the local prescribing information, and routine medical practice in terms of visit frequency and types of assessments performed and only these data will be collected as part of the study. Every effort will be made to ensure all this available data in the patients' chart are captured in the eCRF. The treating physician is asked to complete if possible at every patient visit the appropriate eCRF.

For patients who discontinue prematurely, the reason for discontinuation should be determined.

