The enrollment is defined as the patient's entry into the study; which is the point at which informed consent form is signed. Data will be collected on a minimum of 40 eligible pediatric patients who signed informed consent. These patients should be aged ≥ 10 to <18 years at enrollment, are diagnosed with non-transfusion dependent thalassemia and require to be treated with deferasirox or started deferasirox treatment 12 months or less prior to enrollment. These patients will be followed for up to 5 years from the start of deferasirox treatment. Retrospective data collection will be done for patients whom have started deferasirox 12 months or less prior to enrollment.

The baseline is defined as the timeframe before the patient starts treatment with deferasirox.

In patients who have protocol specified assessments performed prior to the date of first deferasirox treatment, the baseline data will be collected if it is within the following timeframe prior to the date of starting deferasirox treatment (see also table 7-2):

- 1.5 months for all laboratory assessments
- 6 months for vital signs, weight, height, LIC, ECG, ECHO, CMR, ocular and audiometry assessments
- 12 months for pubertal assessments (Tanner stage).

Post baseline data will be collected from the start date of deferasirox and then on for five years.

Investigational treatment

Deferasirox dispersible tablets

Deferasirox dispersible tablet is currently marketed in three dosing strengths (125, 250, 500 mg) and is dosed based on body weight. The currently approved dose range is up to 40 mg/kg/day.

Deferasirox dispersible tablets prescribed by physicians in actual practice setting will be used in accordance with the local label.

Initial deferasirox dose 10 mg/kg/d, 7 d/wk in accordance with the deferasirox prescribing information. Dose titration of deferasirox may be performed based on LIC levels as measured by magnetic resonance imaging (MRI) and/or SF levels and safety markers in steps of 5–10 mg/kg/d as defined by local label requirements.

Deferasirox Film Coated Tablets (FCTs)

Because of the chronic nature of chelation therapy and the importance of patient compliance, an improved deferasirox formulation for oral administration has been developed.

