7.5 Study size

This is a non-interventional study which plans to enroll a minimum of 40 patients. No formal sample size calculation based on the primary endpoint of long-term safety is performed.

Protocols for observational studies (or registry studies) to assess the natural history of a disease or to evaluate the safety of an established product (investigational drug) may not include formal sample size calculations. Data on global epidemiology of NTDT are scarce, see Section 7.2. Also the prevalence of NTDT patients with clinically significant iron overload constitutes a very small percentage of total number of NTDT patients.

Given the small prevalence of the disease under consideration, data on the 40 patients would provide relevant data as described by the computation of probabilities to detect adverse events as shown below. Statistical computations were performed (see table below) to evaluate probabilities to detect at least one patient with an AE given 40 patients and different scenarios of AE incidence rates (Hanley and Lippman-Hand 1983). This table shows a reasonable chance to detect adverse events occurring with an incidence of 5% or higher.

Probability to observe at least one AE for different incidence rates:

Incidence rate of an adverse event	Probability that at least one patient out of 40 experiences the adverse event
3%	0.70
4%	0.80
5%	0.87
6%	0.92
10%	0.99

Incidence rate of an adverse event	Probability that at least one patient out of 40 experiences the adverse event
15%	1.00

7.6 **Data management**

Data will be entered routinely into the study database by the physician/study coordinator.

Novartis personnel (or designated CRO) will review the data entered by investigational staff for completeness and accuracy.

Page 44

Electronic data queries stating the nature of the problem and requesting clarification will be created for all other discrepancies and missing values and sent to the investigational site via the EDC system. Designated physician site staff is required to respond promptly to queries and to make any necessary changes to the data.

Concomitant treatments entered into the database will be coded using the WHO Drug Reference List, which employs the Anatomical Therapeutic Chemical classification system. Medical history/current medical conditions, cause of death and adverse events will be coded using the Medical dictionary for regulatory activities (MedDRA) terminology.

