7.7.4.1 Variable

The primary variable is the proportion of patients having SAEs that are considered to be related to study drug over the period of up to 5 years from the start of deferasirox treatment.

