7.7.4.2 Statistical hypothesis, model, and method of analysis

Counts and frequencies of patients with any drug related SAEs will be provided descriptively on Safety Set overall and by preferred term and system organ class.

In case of high number of SAEs, exposure-adjusted adverse event incidence will also be tabulated.

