- 2. Results in persistent or significant disability/incapacity
- 3. Constitutes a congenital anomaly/birth defect
- 4. Requires inpatient hospitalization or prolongation of existing hospitalization, unless hospitalization is for:
 - a. Routine treatment or monitoring of the studied indication, not associated with any deterioration in condition
 - b. Elective or pre-planned treatment for a pre-existing condition that is unrelated to the indication under study and has not worsened since the start of the drug of interest
 - c. Social reasons and respite care in the absence of any deterioration in the patient's general condition
 - d. Is medically significant, i.e., defined as an event that jeopardizes the patient or may require medical or surgical intervention to prevent one of the outcomes listed above e.g. may require treatment on an emergency outpatient basis for an event not fulfilling any of the definitions of a SAE given above and not resulting in hospital admission
- 5. Transmission of infectious agent via medicinal product

To ensure patient safety, every SAE, regardless of causality assessment, occurring after the patient has provided informed consent and until 30 days after the patient has stopped study later) must be reported to Novartis within 24 hours of learning of its occurrence.

Any SAEs experienced after this 30 day period should only be reported to Novartis if the treating physician or other involved health care professional suspects a causal relationship to the drug of interest.

Recurrent episodes, complications, or progression of the initial SAE must be reported as follow-up to the original episode, regardless of when the event occurs. This report must be submitted within 24 hours of the treating physician or other involved health care professional receiving the follow-up information. An SAE that is considered completely unrelated to a previously reported one should be reported separately as a new event.

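### The primary related-SAE proportion is a crude count over unequal follow-up and partly survivor-selected time, and its exposure adjustment depends on the wrong condition

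*Protocol*

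**What the plan says.** - **Entry (7.2, inclusion criterion 2).** The study takes "Patients currently treated for a maximum of 12 months or patients planned to be treated with deferasirox". An already-treated child must therefore still be on drug at enrolment.
- **Time origin (7.1, 7.7.4.1).** "These patients will be followed for up to 5 years from the start of deferasirox treatment". Section 7.7.4.1 defines its main measure as "the proportion of patients having SAEs that are considered to be related to study drug over the period of up to 5 years", again counted from the start of deferasirox. Data before enrolment are collected retrospectively (7.1, 7.3), and the on-treatment period begins at the first dose (7.7.6.1).
- **Analysis (7.7.4.2).** "Counts and frequencies of patients with any drug related SAEs will be provided descriptively on Safety Set". Then: "In case of high number of SAEs, exposure-adjusted adverse event incidence will also be tabulated". The protocol does not say how many SAEs count as a high number.
- **Withdrawal (7.3, Premature withdrawal).** One mandatory reason for leaving the study is "Deferasirox treatment permanently stopped, except due to stopping rule". Patients may also leave, or be dropped by the physician, at any time.
- **Study size (7.5).** A table of the probability of seeing at least one event in 40 patients leads to the statement "This table shows a reasonable chance to detect adverse events occurring with an incidence of 5% or higher".
- **Limitations (7.9).** Only the absence of a visit schedule and the small sample are listed.

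**The concern.** The endpoint is worded as a proportion over a period of up to 5 years from first dose, but the patients counted are not all observed over that period, at either end.

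At the start, an already-treated child whose related SAE was fatal or led to permanent discontinuation before consent is not eligible. Those who are eligible bring their event-free or non-terminating first months into the count. This is left truncation without delayed entry.

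At the end, a child who stops treatment for good leaves the study and stays in the denominator as though fully observed.

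The condition for adjusting is tied to the number of SAEs. The need to adjust comes from unequal follow-up, which exists whether SAEs are many or few. With about 40 patients the condition may never be met. Long-term safety is the primary objective of a post-authorisation safety study answering a regulatory commitment (7.1), so a low crude percentage is likely to be read as a 5-year risk.

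**Working it through.** **1. The plan's own table.** With 40 patients and an observed proportion p, P(at least one) = 1 − (1 − p)^40. For p = 3, 4, 5, 6, 10 and 15% this gives 0.704, 0.805, 0.871, 0.916, 0.985 and 0.998. All agree with 7.5.

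**2. Inputs.** From the protocol: 40 patients, 5 years from first dose, and up to 12 months of treatment before enrolment. Not given: SAE rate, drop-out rate, share of already-treated patients, share of related SAEs that end treatment, and timing of SAEs. These are assumptions below and are shown as ranges.

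**3. Unequal follow-up alone.** Assume a constant hazard λ and independent exponential withdrawal at rate μ. The crude proportion is λ/(λ+μ) × (1 − exp(−5(λ+μ))). For a true 5-year risk of 5%, λ = −ln(0.95)/5 = 0.01026 per year, and μ = −ln(1 − annual drop-out).

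Example at 10% a year: μ = 0.10536 and λ+μ = 0.11562, so the proportion is (0.01026/0.11562) × (1 − exp(−0.5781)) = 0.0887 × 0.439 = 0.039.

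| Annual drop-out | Crude proportion (true 5%) | P(at least one of 40) |
|---|---|---|
| 0% | 5.0% | 0.87 |
| 5% | 4.4% | 0.84 |
| 10% | 3.9% | 0.80 |
| 15% | 3.4% | 0.75 |
| 20% | 3.0% | 0.71 |
| 25% | 2.7% | 0.66 |

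Under the same model, events divided by patient-years return λ = 0.01026 per year at every drop-out level. That is the case for making the rate unconditional.

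**4. Survivor selection alone.** Let a share s be already treated, with entry uniform over 0 to 12 months, and let a fraction q of related SAEs end treatment and so bar entry. F(t) is the cumulative risk, linear within year 1 and within years 1 to 5. For entry at time e the observed risk is (F(5) − qF(e))/(1 − qF(e)). This is averaged over e, weighted by s, and combined with F(5) for the new starters.

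| True 5-year risk | Mild: s = 25%, q = 0.5, one fifth of risk in year 1 | Severe: s = 100%, q = 1, half of risk in year 1 |
|---|---|---|
| 5% | 4.9% (about 1% lower, relative) | 3.8% (about 24% lower) |
| 10% | 9.9% (about 1% lower) | 7.7% (about 23% lower) |

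Hand check of the severe 10% case at the mean entry time of 0.5 years: F(0.5) = 0.10 × 0.5 × 0.5 = 0.025, so (0.10 − 0.025)/(1 − 0.025) = 0.077.

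**5. Both together.** With half already treated, half of SAEs ending treatment, half the risk in year 1 and 10% annual drop-out, a simulation shows a true 10% as 8.1% and a true 5% as 4.0%.

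**6. What a rate does not repair.** Dividing by patient-years handles unequal follow-up. It leaves survivor time in the denominator, so step 4 needs its own remedy.

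**The case against.** Several stronger readings are tempting, and the protocol does not support them.

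- *SAEs before consent are not captured.* A reader might infer this from section 9, where the 24-hour duty covers "every SAE, regardless of causality assessment, occurring after the patient has provided informed consent". That sentence governs expedited reporting to the sponsor. The same section records adverse events from consent or start of treatment, whichever comes first, and 7.8 has retrospective chart data source-verified. Pre-enrolment SAEs of enrolled patients are therefore collected and counted. Only events that prevented enrolment are lost.
- *The plan ignores exposure.* It does not. Section 7.7.6.2 plans exposure-adjusted tables for treatment-emergent events without any condition, and 7.7.3 reports patient-years. Neither specifies such a table for the primary related-SAE endpoint, and the denominator would still include survivor time.
- *The 7.5 table is wrong.* It is arithmetically correct for a stated observed incidence. It just does not say that this equals the 5-year risk only under full follow-up.
- *The first-year risk is badly understated.* This needs frequent, early, treatment-ending SAEs. The protocol gives no such rate, and its background (section 5) reports no adverse event leading to discontinuation among the paediatric patients of the earlier randomised trial, though there were only 21.

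The best remaining defence is that a crude proportion over actual exposure is a legitimate descriptive summary: permanent discontinuation ends exposure, and an SAE that causes the stop during the study is already counted. That stands as far as it goes. But a summary of risk over actual exposure needs the exposure beside it, which argues for the unconditional rate. Dropping pre-enrolment events from the main count would discard observed related SAEs from a small cohort, so they should stay in.

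**Conclusion.** The point holds in a limited form. As written, the primary proportion can understate the 5-year risk of a drug-related SAE through two mechanisms that both act downwards, and the only adjustment planned for that endpoint depends on an undefined condition unrelated to either.

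The size cannot be derived from the protocol. It is zero if everyone completes 5 years and no related SAE ends treatment before enrolment. Over the assumed ranges, unequal follow-up turns a true 5% into 4.4% to 2.7%, and survivor selection alone takes off about 1% to 24% in relative terms. The drop-out figures assume a constant hazard and withdrawal independent of SAE risk; the selection figures assume uniform entry over 12 months. The selection effect is modest unless most patients are already treated and related SAEs come early and end treatment.

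This is a defect in one endpoint's reporting rule and in the stated limitations. It does not show that safety data are missing for enrolled patients or that the study cannot describe safety.

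**What to change.** 1. In 7.7.4.2, remove the opening condition from the sentence "In case of high number of SAEs, exposure-adjusted adverse event incidence will also be tabulated" and state that the rate of drug-related SAEs per patient-year is always reported beside the proportion.
2. Report the primary endpoint also separately for patients followed from first dose and for patients already on treatment at enrolment. Add a supportive estimate that counts events and time from enrolment (delayed entry). Keep all observed events, including pre-enrolment ones, in the main count.
3. In 7.9, add selection of patients still on treatment at enrolment, and unequal follow-up.
4. In 7.5, add that the tabulated probabilities apply to a 5-year risk only if all 40 patients are followed for the full period.
5. In section 9, make clear how SAEs found retrospectively fit the two different start points for recording and for expedited reporting.

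No new data or patients are needed. The cost is a few extra tables, small subgroups with imprecise estimates, and somewhat less favourable stated figures.
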